Chi square test was used to measure patients' knowledge regarding isotretinoin use at baseline between intervention and control group. It was also used to measure patients' knowledge regarding isotretinoin use at follow-up between intervention and control group. To measure if there was a significant difference in the correct patient knowledge regarding isotretinoin use, the percentage of the correct response for each question was calculated for both groups in baseline and at follow-up. McNamara's test was performed to test if there was a significant difference in knowledge before the intervention and after the intervention in the intervention group, and at if there was a significant difference in knowledge between baseline and follow-up in the control group. In addition, independent t-test was used to compare the knowledge score differences (knowledge score at follow up – knowledge score at baseline) between the intervention group and the control group. Linear regression was conducted to evaluate the effect of the educational intervention on the difference in knowledge score adjusting to variables that were unbalanced at baseline.

Patients Adherence to the Recommendations

Similarly, adherence to recommendations for appropriate uses provided by clinical pharmacists for correct practice was calculated as a total score for each participant. This section consisted of 10 items for all patients, and each item had answers (yes/no). Items were coded according to the answer; the correct (adherent) answer was coded as one (1), while the wrong (not adherent) answer was coded as

zero (0). The adherence score of patients 'compliance with the recommendations ranged between 0 (least adherent) to 10 (most adherent). Average score was evaluated across the intervention and control groups (using t test).

HADS Scale

HADS questionnaire was analyzed based on the scoring system; which consists of fourteen items; seven items each for the depression and anxiety subscale. The score for each item ranges from 0 to 3, and the HADS score ranged from 0 to 21 for depression and the same applied for anxiety.

Chi square test was used to compare HADS items at baseline between intervention and control group. Besides, it was used to compare HADS items at follow-up between intervention and control group. Independent t-test was used to compare the HADS score differences (between baseline and at follow up) between the intervention group and the control group.

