while the remaining were married (3.1%) for both study groups. The vast majority of participants have a bachelor's degree in both the intervention (85%) and control groups (86%). Most of the respondents' area of the residence for both groups was from the Irbid (77.8%) and the rest were from other cities (22.2%). Patients in either intervention or control group had a body mass index (BMI) ranged between 18.5 and 24.9 with a percentage of 68.6% and 73%; respectively.

Regarding health insurance, 96.1% of the intervention group and 98% of the control group were insured. For all study participants, the period since starting to use the drug was no more than the first four months. More than half of the participants took a daily dose of 40 mg of isotretinoin in both intervention (58.3%) and control group (57%). The vast majority of the patients in both study groups (99%) had no chronic disease.

Table 4.1: Baseline demographic and clinical characteristics of the study population

Characteristics	Total		Intervention group		Control group		P-value
	n	%	n	%	n	%	
Gender							
female	179	88.20	91	88.30	88	88	0.939
male	24	11.80	12	11.70	12	12	
Age (years)							
18-20	86	42.40	41	39.80	45	45	0.628
21-25	100	49.20	51	49.50	49	49	
26-30	13	6.40	7	6.80	6	6	
31-35	4	1.90	4	3.90	0	0	
Marital status							
single	196	96.90	98	95.10	98	98	0.265
married	7	3.10	5	4.90	2	2	
Educational level							
school	21	10.30	10	9.70	11	11	0.562
college	4	2	2	1.90	2	2	
bachelor	173	85.20	87	85	86	86	
postgraduate studies	5	2.50	4	3.90	1	1	
Profession							
student	146	71.9	74	71.80	72	72	0.525
Unemployed	25	12.3	10	9.70	15	15	
Non-medical profession	16	7.9	10	9.70	6	6	
Medical profession	16	7.9	9	8.70	7	7	
Residential area							
Irbid	158	77.80	80	77.70	78	78	0.949
Alzarqa'a	3	1.50	2	1.90	1	1	
AL Mafraq	13	6.40	7	6.80	6	6	
Amman	19	9.40	9	8.70	10	10	

Jerash	4	2	2	1.90	2	2	
Ajloun	5	2.50	2	1.90	3	3	
Maan	1	0.50	1	1	0	0	
Monthly income							
below 500 JD	28	13.80	17	16.50	11	11	0.032
500-100 JD	111	54.70	47	45.60	64	64	
above100 JD	64	31.50	39	37.90	25	25	
Health insurance							
yes	197	97	99	96.10	98	98	0.428
No	6	3	4	3.90	2	2	
Strength & dose of isotretinoin per a day (mg)							
10	2	1	2	1.90	0	0	0.612
20	55	27.10	26	25.20	29	29	
30	26	12.80	14	13.65	12	12	
40	117	57.60	60	58.30	57	57	
60	3	1.50	1	1	2	2	
Period since starting the current isotretinoin course (months):							
newly diagnosed	42	20.70	22	21.40	20	20	0.603
first month	42	20.70	23	22.30	19	19	

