second month	51	25.10	26	25.20	25	25	
third month	57	28.1	29	28.20	28	28	
fourth month	11	5.40	3	2.90	8	8	
Body mass index							
under 18.5	23	11.40	11	10.80	12	12	0.783
18.5-24.9	143	70.40	70	68.60	73	73	
25-29.9	28	13.90	15	14.70	13	13	
30-34.9	7	3.50	5	4.90	2	2	
35-39.9	2	1	1	1	1	1	
Total	203	100	103	50.7	100	49.3	

2. General Information Regarding Isotretinoin Use

All patients (100%) were taking isotretinoin based on an authorized prescription. On the other hand, 10.8% of sampled patients had been taking isotretinoin at least once without a prescription prior to current use; 10.7% of intervention group and 11% of control group with P-value = 0.941. While 89.2% had never used isotretinoin before without prescription; 89.3% of the intervention group and 89% of the control group. 59.2% of the intervention group and 67% of the control group did not visit a dermatologist for acne problems for the first time but did so several times before starting isotretinoin with a P-value=0.251.

Participants were asked to answer two questions regarding laboratory testing (liver function test and lipid profile test), whether these tests were required to be performed, and if they did check them before starting treatment. Results showed that 98.1% of intervention group and 98% of control group

were required to undergo testing with $P\text{-value}=0.976$, while 97.1% of the intervention group and 97% of the control group with $P\text{-value}=0.971$ were checked these tests. Approximately 69.5% of enrolled patients said that their physicians informed them about the expected side effects of isotretinoin and how to manage it; 72.8% of the intervention group and 66% of the control group with $P\text{-value}=0.327$.

During the questionnaire, participants were asked to answer two questions about the impact of having acne on their daily, psychological and social life, about the severity of their acne condition, and results are summarized in Figure 2 and Figure 3; respectively.

[figure not shown]

Figure 2: The impact of acne on daily, psychological, and social life.

[figure not shown]

Figure 3: The severity of acne condition as reported by participants.

3. Patients Knowledge about Isotretinoin Use

Patients' knowledge about isotretinoin treatment for both groups was assessed at baseline and at the

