I adhere to make lipid profile test during isotretinoin use			
yes	102 (99)	98 (98)	0.618
no	1 (1)	2 (2)	
I adhere to use sunblock when going out during isotretinoin use			
yes	98 (95.1)	91 (91)	0.244
no	5 (4.9)	9 (9)	
I adhere to take isotretinoin with fatty foods			
yes	88 (85.4)	62 (62)	< 0.001
no	15 (14.6)	38 (38)	
I adhere not to donate blood during isotretinoin use			
yes	103 (100)	43 (43)	< 0.001
no	0 (0)	57 (57)	
I adhere not to make laser or wax during isotretinoin use			

yes	87 (84.3)	51 (51)	< 0.001
no	16 (15.7)	49 (49)	

Results showed that 86.4% of the intervention group compared to 69% of control group were adherent to the use of eye drop, and the difference was statistically significant (P-value=0.003). The adherence to using body lotion was higher in the intervention group (46.6%) compared to the control group (28%) with a P-value=0.006. On the other hands, there were no significant differences between both groups regarding the use of lip balm and sunblock.

For the two questions about adherence to laboratory monitoring (i.e., the liver function test or the lipid profile test), the rate of adherence was high in both group (99% for the intervention group and 98% for the control group) with no significant statistical difference.

The results of responses to the last three questions about adherence (taking the medication with or after fatty meals, adherence to not donate blood, and not to make laser or wax during treatment) were significantly different between the control and intervention group with P-value <0.001.

5. HADS Scale

HADS-Anxiety score and HADS-Depression score were tested at baseline and at follow-up after three months. At baseline, the mean HADS-Anxiety score for both groups was 7.8079 ± 4.159 , which slightly improved to 7.5862 ± 3.28 at follow-up, which was statistically not significant. Likewise, the mean HADS-Depression score was 6.773 ± 3.709 , while at follow-up it became 7.0148 ± 3.1029 and it was statistically not significant. The responses for intervention and control group at follow-up (intervention vs. control group) are indicated in **Table 6**.

Table 6: HADS anxiety and depression score at follow-up

	Intervention group n (%)	Control group n (%)	P-value
I feel tense or 'wound up.'			
most of the time	4 (3.9)	2 (2)	0.006
a lot of the time	20 (19.4)	7 (7)	
from time to time	54 (52.4)	75 (75)	
not all time	25 (24.4)	16 (16)	
I get a sort of frightened feeling like 'butterflies' in the stomach:			

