- It's good.
- Acceptable
- Weak

26. What is the impact of the side effects on your daily life and your usual activities?

- Big effect
- moderate effect

- Weak effect
- There's no effect.

27. Was the menstrual cycle affected during treatment?

- Yes
- No

- If yes, what is the impact?

- getting late
- getting early
- became heavy
- became light
- its duration became longer
- its duration became shorter

28. Was your treatment affected during the Corona period?

- Big effect
- moderate effect
- Weak effect
- There's no effect.

- If yes, what is the impact?

- Getting the medication
- adherence to medication
- Going for monthly doctor reviews
- adherence to periodic tests

29. Do you think you needed to explain more about the drug in general?

- Yes
- No

30. Do you think you needed to explain more about the drug in terms of the method of use?

- Yes
- No

31. Do you think you need edited more explanations about the side effects of the drug and how to avoid it?

- Yes
- No

32. Do you have any feedback regarding this questionnaire?

- Yes

No

Please answer the following questions regarding adherence to recommendations provided by clinical pharmacist.

	yes	no	I do not know	Not applicable
I adhere to drink plenty of water during isotretinoin use				
I adhere to use eye drop during isotretinoin use				
I adhere to use lip balm during isotretinoin use				
I adhere to use body lotion during isotretinoin use				
I adhere to make laboratory monitoring (AST & ALT) during isotretinoin				
I adhere to make lipid profile test during isotretinoin use				
I adhere to use sunblock when going out during isotretinoin use				
I adhere to take isotretinoin with fatty foods				
I adhere not to donate blood during isotretinoin use				
I adhere not to make laser or wax during isotretinoin use				
I adhere not to breastfeed my child during treatment:				
I adhere to do a monthly pregnancy test				

Please answer the following questions regarding adherence to the medication?

	At all	Rarely	Sometimes	Usually,	Always
Do you forget to take your meds?					
Do you skip medication when you feel better?					
Do you skip taking medications when they're worse after taking medications?					
Have you run out of your medications?					
In general, do you adhere to what your doctor or pharmacist tells you about your lifestyle (food, exercise, smoking...) I don't think					
Can you please tell us what are the most common reasons for not taking your medications?					

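### The follow-up adherence items have no defined recall window, and 161 of 203 patients were already on their isotretinoin course at baseline, so behaviour before randomisation can be scored as outcome

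*Combined protocol and SAP*

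**What the plan says.** - **Recommendation items** (Results, section 4, Table 5; Appendix 3, part B). Ten yes/no statements in the present tense are scored, for example "I adhere not to make laser or wax during isotretinoin use". Nine mention the time on the drug; the fatty-food item does not. The block's heading on the form refers to advice given by the clinical pharmacist. Neither the heading nor any item gives a start point.
- **Medication items** (Appendix 3, part B). These use a five-point frequency scale with no period stated, for example "Have you run out of your medications". Table 8 prints that item in the present tense.
- **Analysis** (Data analysis, Patients Adherence to the Recommendations). The ten items are summed: "Average score was evaluated across the intervention and control groups (using t test"). The comparison is at follow-up only. The baseline questionnaire (Appendix 3, part A) has no adherence items.
- **Time on drug at baseline** (Results, section 1). "For all study participants, the period since starting to use the drug was no more than the first four months". Table 4.1 gives the distribution under "Period since starting the current isotretinoin course (months"), and only 42 patients are listed as newly diagnosed.
- **Timing.** The Study Protocol plans measurement one and three months after isotretinoin is started. Results, section 3 describes follow-up as three months after the education session.

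**The concern.** In a patient who starts isotretinoin at enrolment, a question about the time on the drug covers almost exactly the period after randomisation. For most patients enrolled here it need not. A patient who had laser or wax treatment in month 1, was randomised in month 3 and stopped after the education session can fairly answer either way, depending on the period she has in mind.

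Two consequences follow, in opposite directions. If both arms answer for the whole course, behaviour that the education could not have influenced is counted in both, and the difference shrinks. If intervention patients answer for the time since the session while controls answer for the whole course, the difference grows. The form leaves room for the second case: its heading on the pharmacist's advice offers a natural starting point to the intervention arm only, because controls received no such advice. With no baseline adherence measure, earlier behaviour cannot be separated out afterwards. Adherence to recommendations is the outcome named in the trial's title.

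**Working it through.** **Inputs (Table 4.1), after checking the tables against themselves.**

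| Time on course at baseline | Total | Intervention | Control |
|---|---|---|---|
| newly diagnosed | 42 | 22 | 20 |
| first month | 42 | 23 | 19 |
| second month | 51 | 26 | 25 |
| third month | 57 | 29 | 28 |
| fourth month | 11 | 3 | 8 |
| Sum | 203 | 103 | 100 |

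The chi-square test on these rows gives P = 0.602 (0.603 stated). The item counts in Table 5 give mean scores of 879/103 = 8.534 (8.534 stated) and 665/100 = 6.65 (6.64 stated).

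**Step 1. Patients already on the course.** 42 + 51 + 57 + 11 = 161, and 161/203 = 79.3%. By arm: 81/103 = 78.6% and 80/100 = 80.0%, so time on drug is balanced. If *first month* includes patients starting that day, the count could be as low as 161 − 42 = 119.

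**Step 2. Share of a whole-course window that precedes enrolment.** Assume follow-up three months after enrolment: 203 × 3 = 609 patient-months after it. The months before depend on how the *n*th month is counted:

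- *n* full months: 42×0 + 42×1 + 51×2 + 57×3 + 11×4 = 359; 359/(359 + 609) = 359/968 = 37%.
- Mid-month: 42×0.5 + 51×1.5 + 57×2.5 + 11×3.5 = 278.5; 278.5/887.5 = 31%.
- Completed months: 51×1 + 57×2 + 11×3 = 198; 198/807 = 25%.

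**Step 3. Do the answers fit one whole-course reading in both arms?** Take the two abstention items. Assume a constant monthly hazard *h* of a first breach, the same behaviour before enrolment in both arms, and both arms answering for the whole course. With *m* the months before enrolment and *c*, *i* the control and intervention counts, solve Σ *c*(1 − e^(−*h*(*m*+3))) = observed control breaches for *h*. The intervention breaches expected before the session are then Σ *i*(1 − e^(−*hm*)).

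| Item | Control non-adherent | *h* per month | Expected before session, intervention | Reported in total, intervention |
|---|---|---|---|---|
| Laser or wax | 49/100 | 0.142 to 0.170 | 13.6 to 20.8 | 16/103 |
| Blood donation | 57/100 | 0.179 to 0.214 | about 17 to 25 | 0/103 |

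The laser/wax result is compatible with the assumptions; the blood-donation result is not. At baseline 67 of 103 intervention patients believed donation was allowed (Table 2), yet none reports a breach. In the control arm the 43/57 adherence split on blood donation equals the 43/57 knowledge split in Table 3. These are marginal totals only, but they suggest that answers may follow present belief, intention or practice.

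**Step 4. Sensitivity of the medication result.** Non-adherent: 13/103 v 23/100. The Pearson chi-square is 203 × (13×77 − 90×23)² / (103 × 100 × 36 × 167) = 3.75, P = 0.053, as stated. Reclassifying one patient gives P = 0.032 (12/103 v 23/100) or 0.036 (13/103 v 24/100); in the other direction 0.083 (14/103 v 23/100) or 0.077 (13/103 v 22/100). This shows how close the result is to the threshold. It does not show that any answer was misclassified.

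**The case against.** The strongest reply is that the items do not ask about the whole course. They are in the present tense, under a heading about advice a patient can follow only once it has been given, and the reference to time on the drug may simply state when the advice applies. Current practice is at least as natural a reading. This stands, and it is why the defect is an undefined window and not a wrong one.

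Second, a single past act can breach only two of the ten items for good. Water, eye drops, lip balm, lotion, sunblock and fatty food are habits that a patient can truthfully report as kept after improving, and the two laboratory items are at 98% to 99% in both arms. For the medication items, *Rarely* counts as adherent: running out is 67 + 31 = 98 of 103 adherent in the intervention arm. One old lapse need not change a patient's category. This also stands, and it limits how much of the score is exposed.

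Third, time on drug is balanced and allocation cannot affect earlier behaviour, so carry-over should only dilute. That is right if both arms use the same window. Randomisation balances time on drug; it does not settle how an unanchored question is understood after one arm has had an education session.

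A reader might infer from Step 3 that either nearly all the intervention arm's laser/wax breaches predate the education or the arms used different windows. The documents do not support that. The calculation presupposes the whole-course reading, and it leaves out the simplest alternative: both arms report current practice, and the education changed it (16/103 v 49/100).

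**Conclusion.** The point holds as a gap in the wording of the outcome. The window is undefined for nine recommendation items that refer only to time on the drug, for the fatty-food item, which gives no period, and for the medication items. Of 203 patients, 161 (79%) had time on the course before baseline that such wording can take in, and there is no baseline measure to remove it.

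The size is conditional. Under a common whole-course reading, with follow-up three months after enrolment, 25% to 37% of the patient-months asked about precede enrolment, and the bias is towards no difference. Inflation requires the arms to read the items differently; the heading makes that possible, and nothing reported shows it. No corrected effect can be computed, because Table 5 is not split by time on drug.

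A reader might go further and conclude that the window explains the difference of 8.53 v 6.64, or that the outcome does not measure behaviour after the intervention at all. Neither follows: common carry-over cannot create a difference between arms, and patients may have answered for current practice throughout. This is a change that should be made, with medium confidence.

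**What to change.** **Questionnaire.** On the follow-up form, put one stem, *Since your first study interview...*, above both the recommendation block and the medication block, in both arms, in place of the words *during isotretinoin use*. Both arms then have the same starting point and do not depend on the heading about the pharmacist's advice. Cost: one line of wording.

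**Data in hand.** Show Table 5, the total score and Table 9 again for the 42 newly diagnosed patients (22 v 20), labelled as a sensitivity analysis. If *newly diagnosed* means not yet started on the current course, their window lies wholly after randomisation. Cost: one extra table, and imprecise estimates. With these numbers, power for a laser/wax difference as large as that reported (84.3% v 51%) is about 65%, so a non-significant item result should not be read as no effect. For the total score, a difference of 1.894 with an SD of about 1.0 would almost certainly be detected.

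**Reporting.** State that the answers of the other 161 patients may include time before randomisation.

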After the informed consent (see appendix 1) is taken from each patient who agreed to participate in the study, the participants will be randomly assigned to either an intervention group or a control group. Intervention group will consist of the patients who will receive the educational process (recommendations) about isotretinoin by clinical pharmacists additionally to the usual routine care (education about isotretinoin provided by the physician). Control group will consist of the patients who will receive the usual routine care. Both patients and physicians are unaware of patients' assignment in both groups.

The main task of the clinical pharmacist is to educate patients in intervention group by providing them all information about isotretinoin that can serve the patient during the treatment period, which includes: the degree of the importance of adherence to the drug and the recommendations, the correct method of taking it, the importance, and when, of doing periodic laboratory tests (lipid profile, liver enzyme test, and pregnancy test), and explanation of common side effects, how to avoid and deal with them, and what are the cases in which the drug should be stopped. The detailed information on the recommendation for managing side effects that will be used to educate the patients are provided in Appendix 2.

Patient's adherence to the recommendations, awareness and side effects managements for both groups will be measured through a set of questions adapted from a validated questionnaire after one month and three months of isotretinoin initiation (Appendix 3). The validated questionnaire was adopted from a previous study on patients' knowledge about isotretinoin therapy use in Jordan. The permission to use the questionnaire was obtained from the researcher.

The questionnaire is composed of 41 questions related to: demographics, side effects, physician and clinical pharmacist practice, recommendations and contraindications according to current guidelines, and patients' commitment. In addition, the Hospital Anxiety and Depression Scale (HADS) [22], will be used to evaluate depressive and anxiety symptoms at baseline and during the follow up period in each group. Finally, clinical improvement in acne will be evaluated three months after initiating the treatment from the view of physicians as well as the patients themselves.

Location and safety considerations

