HADS scores were categorized into three categories based on the abnormality classification; normal (less than eight), borderline abnormal (between eight and eleven) and abnormal (above eleven). Chi square test was used to evaluate the association between HADS score categories and intervention control status at baseline and at follow up.

Patients Adherence to Medication

The percentages (%) of patients' adherence to medication and non-pharmacological adherence were calculated by dividing the number of adherent patients by the total number of patients in both groups. According to the final question, the reasons behind the patient's non-adherence were themed into three distinct groups (forgetfulness, run out, and unavailability of isotretinoin). The frequency (%) of each group was calculated by dividing the number of times each category has occurred over the total number of patients and multiplying by 100. Chi-square test was conducted to evaluate the association between adherence status and patient intervention control status.

Results

1. Baseline Questionnaire Results

A total of 207 patients using isotretinoin in Jordan were randomly recruited to participate in the study. About four patients missed answering the phone in the follow-up phase, so they were excluded from the study. The response rate was 96.7% and 203 patients completed the study as shown in **Figure 1**.

[figure not shown]

Figure 1: Patient recruitment flowchart

1. Demographics of Respondents

The demographics of the participants are summarized in **Table 1**. All baseline demographic and clinical characteristics of the study participants were not statistically different between intervention and control group except for monthly income with P -value=0.032. Most respondents were female ($n=179$, 88.2%) compared to male ($n=24$, 11.8%) in both groups. Most of the patients were in the age group of 18-25 years, and the $mean \pm SD$ of age for the intervention group was 21.68 ± 3.21 and 21.36 ± 2.6 for the control group. Regarding marital status, 96.9% of the participants were single

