The average difference in anxiety score (difference between baseline and follow up) was not significant between intervention and control group (P-value=0.238) Similarly, the average difference in depression score was not significant between intervention and control group (P-value=0.323).

HADS score categories for both anxiety and depression subscales were not associated with the intervention control status at baseline nor at follow up. **Table 7** summarizes the results for follow-up.

Table 7: Comparison between intervention and control groups in HADS percentages at baseline and follow-up

	HADS-baseline (%)		P-value	HADS-follow up (%)		P-value
	Intervention	Control		Intervention	Control	
Anxiety score						
less than 8	45.60	55	0.283	49.50	55	0.536
8_11	24.30	24		26.20	27	
above 11	30.10	21		24.30	18	
Depression score						
less than 8	55.30	64	0.108	58.30	64	0.288
8_11	21.40	24		20.40	23	
above 11	23.30	12		21.40	13	

6. Patient Adherence

7. Pharmacological Adherence

The descriptive results of drug-taking behavior and the adherence at follow-up for all patients are presented in **Table 8**.

Table 8: Descriptive statistics of patient's answer to adherence questionnaire

	Intervention group	Control group
--	--------------------	---------------

	n (%)	n (%)
Do you forget taking your medication		
Never	42 (40.8)	31 (31)
Rarely	51 (49.5)	51 (51)
sometimes	10 (9.7)	18 (18)
Usually	0 (0)	0 (0)
Always	0 (0)	0 (0)
Do you stop your medication when you feel better		
Never	103 (100)	98 (98)
Rarely	0 (0)	2 (2)
sometimes	0 (0)	0 (0)
Usually	0 (0)	0 (0)
Always	0 (0)	0 (0)
Do you stop your medication when you feel worse		
Never	103 (100)	98 (98)
Rarely	0 (0)	2 (2)
sometimes	0 (0)	0 (0)
Usually	0 (0)	0 (0)
Always	0 (0)	0 (0)
Do you run out of your medication		
Never	67 (65)	43 (43)
Rarely	31 (30.1)	48 (48)
sometimes	5 (4.9)	9 (9)
Usually	0 (0)	0 (0)
Always	0 (0)	0 (0)
Do you adhere to lifestyle recommendations		
Never	0 (0)	1 (1)
Rarely	1 (1)	0 (0)
sometimes	2 (1.9)	1 (1)
Usually	51 (45.5)	78 (78)
Always	49 (47.6)	20 (20)

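### HADS subscale scores are given only as means over both arms, and the planned between-arm comparison of change only as P-values without estimate, direction or interval

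*Combined protocol and SAP*

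**What the plan says.** The Study Protocol part says that HADS "will be used to evaluate depressive and anxiety symptoms at baseline and during the follow up period in each group". The HADS paragraph of the Data analysis section names the score-level test: "Independent t-test was used to compare the HADS score differences (between baseline and at follow up"), intervention against control. It also plans chi-square tests on the items and on three score bands.

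Results section 5 opens with the subscale means. At baseline "the mean HADS-Anxiety score for both groups was 7.8079 ± 4.159"; at follow-up it was 7.5862 ± 3.28. Depression went from 6.773 ± 3.709 to 7.0148 ± 3.1029. All four figures combine the two arms.

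The between-arm result is: "The average difference in anxiety score (difference between baseline and follow up) was not significant between intervention and control group (P-value=0.238"). Depression is treated alike, with P=0.323.

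Table 6 gives every follow-up item by arm. Table 7 gives the score bands by arm at both visits. No subscale mean, SD, mean change, difference or confidence interval is given by arm.

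**The concern.** The question a randomised comparison can answer is whether the arms differ. A mean over both arms, before and after, removes that contrast. The sentences that restore it report non-significance and nothing else, so a reader is likely to take them as evidence of no difference without seeing what size of difference remains possible, or in which direction.

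Other scored outcomes in the same document are reported more fully. Mean change in knowledge is given by arm (2.835 ± 1.329 v 0.530 ± 0.784), and so is the recommendation score (8.534 ± 0.905 v 6.64 ± 1.039). HADS is the only mood measure in the trial, and Appendix 2 itself lists depression among the possible effects of isotretinoin. The comparison therefore deserves at least the same reporting.

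**Working it through.** **Inputs.** Item counts by arm come from Table 6. The scoring rule is in the Data analysis section ("The score for each item ranges from 0 to 3"; "the HADS score ranged from 0 to 21 for depression and the same applied for anxiety"), with the direction of each item taken from the key in Appendix 3, so that positively worded items are reversed. Higher is worse, as the bands confirm: "normal (less than eight), borderline abnormal (between eight and eleven) and abnormal (above eleven"). The arm sizes, 103 and 100, are in the last row of the baseline table ("Total 203 100 103 50.7 100 49.3").

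**Step 1: reproduce the printed means.** Item score sums, in Table 6 order:

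| Subscale | Intervention (n=103) | Control (n=100) |
|---|---|---|
| Anxiety | 106+117+145+105+157+53+136 = 819 | 95+92+128+100+139+42+125 = 721 |
| Depression | 114+136+20+103+100+134+131 = 738 | 109+126+14+90+91+123+133 = 686 |

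Anxiety: (819 + 721)/203 = 1540/203 = 7.5862. Depression: (738 + 686)/203 = 1424/203 = 7.0148. Both match the printed follow-up means to four decimals, so the scoring can be relied on.

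**Step 2: follow-up means by arm.**
- Anxiety: 819/103 = 7.95 v 721/100 = 7.21; difference 0.74.
- Depression: 738/103 = 7.17 v 686/100 = 6.86; difference 0.31 (7.165 - 6.860 = 0.305).

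**Step 3: approximate intervals.** The arm SDs are not printed, so I use the both-arm SDs. SE = SD × √(1/103 + 1/100) = SD × 0.1404, and the t quantile on 201 df is 1.97.
- Anxiety: SE = 3.28 × 0.1404 = 0.460; 0.74 ± 0.91 gives about -0.17 to 1.65.
- Depression: SE = 3.1029 × 0.1404 = 0.436; 0.31 ± 0.86 gives about -0.55 to 1.16.

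**Step 4: was the gap there at baseline?** Table 7, per cent scoring above 11:

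| Subscale | Baseline, intervention v control | Gap (points) | Follow-up, intervention v control | Gap (points) |
|---|---|---|---|---|
| Anxiety | 30.1 v 21 | 9.1 | 24.3 v 18 | 6.3 |
| Depression | 23.3 v 12 | 11.3 | 21.4 v 13 | 8.4 |

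The share below 8 rose in the intervention arm (anxiety 45.6 to 49.5, depression 55.3 to 58.3) and stayed at 55 and 64 in the control arm.

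**Step 5: what the bare P-values leave open.** The size of the change difference depends on the baseline to follow-up correlation r, which is not given. I assume r from 0.2 to 0.8. SD of change = √(s0² + s1² - 2·r·s0·s1), from the printed both-arm SDs. The absolute difference is the t value for the printed P (about 1.18 for 0.238, about 0.99 for 0.323) times SD of change × 0.1404.

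| r | Anxiety: SD of change | Anxiety: absolute difference (95% half-width) | Depression: SD of change | Depression: absolute difference (95% half-width) |
|---|---|---|---|---|
| 0.2 | 4.75 | 0.79 (1.32) | 4.33 | 0.60 (1.20) |
| 0.5 | 3.80 | 0.63 (1.05) | 3.45 | 0.48 (0.95) |
| 0.8 | 2.50 | 0.41 (0.69) | 2.23 | 0.31 (0.62) |

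The sign is not given, and it matters. For anxiety at r = 0.5, the baseline gap would be 0.74 + 0.63 = 1.37 if change favoured the intervention, but 0.74 - 0.63 = 0.11 if it favoured control.

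**The case against.** The strongest reply is that the comparison by arm is in the document. Table 6 prints all 14 items by arm, Table 7 prints the bands by arm at both visits, and the planned tests on items, change and bands are all reported at follow-up. The protocol's promise of evaluation in each group does not literally promise means or intervals, and the word for the small fall in anxiety is arithmetically true and at once qualified as non-significant. All of this stands. It makes the point one of incomplete reporting: nothing has been concealed and no planned test was left out. It does not supply the missing estimate. A reader must score 14 items of mixed direction by hand to get the follow-up difference, and cannot get the change difference at all.

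A reader who does that scoring will find the intervention mean higher on 13 of 14 items (all but the book, radio or TV item) and might infer that the education session raised distress. The documents do not support this:
- The items are correlated answers from the same patients, so the count is not 14 separate signals.
- The 13 gaps run only from 0.02 to 0.22 on a 0 to 3 scale.
- On seven of those 13 items the intervention arm also has the larger share in the best category.
- Both subscale intervals include zero.
- The imbalance in Table 7 was larger before the intervention than after it.

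**Conclusion.** The point holds as a reporting gap that should be closed. The subscale means are given only over both arms, and the planned comparison of change has no estimate, direction or interval. The unadjusted follow-up differences are 0.74 points for anxiety (about -0.17 to 1.65) and 0.31 for depression (about -0.55 to 1.16), on subscales of 0 to 21. These rest on the Appendix 3 scoring direction, which reproduces both printed means, and on the both-arm SDs standing in for the arm SDs.

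They are not estimates of the intervention effect, because they ignore baseline and the arm means at baseline cannot be recovered. It would be equally unsupported to predict that fuller reporting will look worse for the intervention. The direction of the change difference is not printed, and the band shifts in Table 7, if anything, lean the other way.

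**What to change.** In Results section 5, replace the before-after sentences over both arms with one small table. For each subscale, give the mean (SD) by arm at baseline and follow-up, the mean change (SD) per arm, and the between-arm difference at follow-up adjusted for baseline HADS (ANCOVA) with its 95% CI. Keep the planned t-test of change, now with its estimate and interval, and label the ANCOVA as an addition to the plan. A raw follow-up difference alone would not do, given the baseline imbalance in Table 7.

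Word the conclusion by the differences that the adjusted interval excludes, instead of by P alone. The cost is one table and a few sentences from data already in hand; nothing new has to be collected.
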